12.4 Recording of AEs and SAEs

All AEs, regardless of seriousness, severity, or presumed relationship to study treatment, must be recorded using medical terminology in the eCRF and/or other sources. Whenever possible, diagnoses should be given when signs and symptoms are due to a common etiology (e.g., cough, runny nose, sneezing, sore throat, and head congestion may be reported as "upper respiratory infection"). Investigators must record in the eCRF the date of onset of the event, their opinion concerning the relationship of the AE to study therapy. Severity of the event, whether the event is serious or nonserious, actions taken to manage the event, the outcome of the event, and date of resolution where applicable.

Any change to the severity of an AE must be recorded as a separate AE, ensuring that the end date and time of the preceding AE matches the start date and time of the subsequent AE, so that the overall duration of the AE is continuous.

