Efficacy	Primary cognitive assessments will be the: • Alzheimer's Disease Assessment Scale-Cognitive Subscale test (ADAS-Cog) Secondary efficacy assessment will be the: • Alzheimer's Disease Co-operative Study Mild Cognitive Impairment Activities of Daily Living (ADCS-MCI-ADL24) • Depression Anxiety Stress Scale (DASS-21) PET Scan • visual assessment of amyloid load • quantitative assessment of amyloid burden MRI Scan • volumetric changes in the brain • cerebral amyloid abundance
Statistical Analysis	
Overview	Analysis of all primary and secondary endpoints contrasting Lorelco TM and placebo, after adjusting for covariates, will use mixed effects-regression with 'random' intercepts and slopes (as has been used for power calculations). Mean differences and associated 95% confidence intervals will be presented for the 'fixed' effect Lorelco TM treatment.
Safety and Tolerability	The secondary analysis will assess the safety and tolerability of Lorelco™ in patients with mild to moderate Alzheimer's disease using the safety population. Treatment emergent adverse events (TEAEs) will be grouped by Medical Dictionary of Regulatory Activities (MedDRA) system organ class and preferred term and summarized by presenting the number and percentage of patients who experience each AE and the number of AEs. Summaries by severity (graded according to the NCI-CTCAE v5.0 [or higher]) and relationship to study drug will be provided for all TEAEs. Where applicable, laboratory test results will be graded and summarized according to the NCI-CTCAE v5.0 (or higher). The actual values and changes from baseline at each post-baseline time point for clinical laboratory parameters, vital signs and ECG parameters will be summarized by visit and timepoint (where applicable).
Pharmacodynamics	

Protocol Version 4, 06 OCT 2021

Confidential

Page 10 of 70

Efficacy

The primary analysis was an intention-to-treat analysis of all randomized participants. Data will be analysed using both Generalised Estimating Equations (GEE) and Bayesian Analysis. The analysis of primary endpoints will use linear mixed-effects models, with random slopes and intercepts.

The Alzheimer's Disease Assessment Scale's cognitive subscale (ADAS-Cog) is the standard primary cognitive outcome measure for evaluating treatments in clinical trials of mild-to-moderate AD.

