12.3 Procedures and Time Period for Detecting Adverse Events

The Investigator (or designee) is responsible for detection, recording and reporting of events that meet the criteria and definition of AEs.

As a consistent method of soliciting AEs, the participant shall be asked a non-leading question such as: "How do you feel?".

Detection and recording of study related AEs and SAEs extends from the signing of the consent form until completion of the last study related procedure (including follow-up for safety assessments).

Any AE reported or observed after the start of dosing with any study treatment until completion of the last study related procedure (includes follow-up for safety assessments) will be recorded as a treatment-emergent AE.

Any change in health status that is reported or observed after informed consent but prior to starting study treatment and is deemed by the study Investigator to be "not related" to study procedures, will be documented as medical history.

Any pre-existing conditions or signs and/or symptoms present in a patient prior to any involvement in the study (i.e., before informed consent) should be recorded as medical history. In addition, any change in health status, which is reported after informed consent but started prior to informed consent by the volunteer, will be documented as medical history.

Any worsening of a pre-existing condition that occurs following informed consent will be recorded as an AE.

A post-study AE/SAE is defined as any event that occurs outside of the nominal AE/SAE study detection period. Investigators are not obligated to actively seek AEs/SAEs in former study participants. However, if the Investigator learns of any SAE, including a death, at any time after a participant has completed the study and he/she considers the event reasonably

Protocol Version 4, 06 OCT 2021

Confidential

Page 45 of 70

	Study Protocol
Curtin University	Protocol No.: PIA-2020

related to the study treatment, the Investigator will promptly notify the Sponsor.

Patients must be provided with an "Emergency Wallet Card" indicating the name of the study treatment, the study number, the Investigator's name, and emergency contact number.

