13.4 Safety and Tolerability Analyses

Assessment of safety and tolerability is a seondary objective of the study. The analysis will assess the safety and tolerability of LorelcoTM in patients with mild to moderate AD using the safety population.

Safety and tolerability will be assessed through AE, clinical laboratory, vital signs, ECG, and physical examination data. AEs that occur at or after the first dose of Lorelco[™] or placebo will be classified as treatment-emergent adverse events (TEAEs).

The original terms used in the eCRF by Investigators to identify AEs will be coded by system organ class and preferred term using the current version of the Medical Dictionary for Regulatory Activities (MedDRA).

TEAEs will be grouped by system organ class and MedDRA preferred term and summarized by presenting the number and percentage of subjects who experience each TEAE and the number of TEAEs. Summaries by severity (graded according to the NCI-CTCAE v5.0 [or higher]) and relationship to Investigational Product will be provided for all TEAEs. Data listings will also be provided for any deaths, SAEs, and AEs leading to discontinuation of the study.

The actual values and changes from baseline at each post-baseline time point for clinical laboratory parameters, vital signs and ECG parameters will be summarized by visit and timepoint (where applicable). Where applicable, laboratory test results will be graded and summarized according to the NCI-CTCAE v5.0 (or higher). Baseline will be defined as the last assessment prior to the first dose of LorelcoTM/ placebo.

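### Recording every grade change as a separate AE inflates the number of TEAEs and the severity summary, and the TEAE definition lets an improving pre-dose AE count as treatment-emergent

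*Protocol*

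**What the plan says.** Three parts of the protocol act together.

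- **Recording (12.4).** "Any change to the severity of an AE must be recorded as a separate AE". The end of one record must match the start of the next, "so that the overall duration of the AE is continuous". The rule makes no distinction between a rise and a fall in grade.
- **Summaries (13.4 and synopsis).** TEAEs are summarised "by presenting the number and percentage of subjects who experience each TEAE and the number of TEAEs". The synopsis gives the same pair of measures: "the number and percentage of patients who experience each AE and the number of AEs". Summaries by CTCAE grade and "relationship to Investigational Product will be provided for all TEAEs".
- **Treatment emergence (12.3 and 13.4).** Section 13.4 classes as treatment-emergent the "AEs that occur at or after the first dose of Lorelco" or placebo. Section 12.3 has "Any AE reported or observed after the start of dosing with any study treatment", up to the last study procedure. Neither asks whether the event is new or worse.

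Section 12.3 also limits what can be an AE before dosing. Conditions that began before consent are medical history, and so are changes between consent and first dose judged unrelated to study procedures. A worsening of a pre-existing condition after consent is an AE.

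**The concern.** The recording rule turns one clinical event into several AE records, and the summaries are defined on AEs. Nothing in the protocol says that the segments of one event count once, or that a subject enters the severity table at the worst grade. The highest-severity rule in 12.2.1 concerns several aspects of one AE, not its grade over time.

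Incidence, type and severity of AEs is a stated secondary endpoint. The event count and the severity table would partly reflect how often grades move and how often they are asked about. There are many chances to record a move: 12.6 has ongoing AEs reviewed at later contacts, and the schedule in Appendix 1 marks AE review at 19 contacts from Week 3 to Week 108. The trial stopping criteria in 6.6 also refer to unexpected severity or frequency of adverse effects, so inflated counts could colour more than the final report.

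The open TEAE definition adds a second fault. An AE present before first dose that eases afterwards generates a record starting after first dose, and that record meets the definition in 13.4.

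**Working it through.** The protocol states no AE rate or count, so there is no figure to reproduce. The check applies the written rules to example grade histories and then shows a range under stated assumptions.

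**Step 1: records per event.** Under 12.4, records for one continuous event = 1 + number of grade changes. Under 13.4, every record starting at or after first dose is a TEAE.

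| Grade history of one event | AE records | TEAEs as written | TEAEs if counted once and only if new or worse | Subjects with the term, as written |
|---|---|---|---|---|
| On treatment, constant Grade 1 | 1 | 1 | 1 | 1 |
| On treatment, 1-2 | 2 | 2 | 1 | 1 |
| On treatment, 1-2-1 | 3 | 3 | 1 | 1 |
| On treatment, 1-2-3-2-1 | 5 | 5 | 1 | 1 |
| Pre-dose Grade 2, Grade 1 after dose | 2 | 1 | 0 | 1 (should be 0) |
| Pre-dose Grade 2, unchanged | 1 | 0 | 0 | 0 |

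For events that begin on treatment, the event count is wrong and the subject count is right. The 1-2-1 event also enters the severity summary at Grade 1 twice and Grade 2 once, where its worst grade is 2. In the fifth row the subject count is wrong too.

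**Step 2: who can be in the fifth row.** By 12.3, only a pre-dose event related to study procedures, or a post-consent worsening of a pre-existing condition. Pre-dose means before the first run-in placebo capsule, because everyone takes placebo in Weeks 1 and 2 and the definition in 13.4 starts with the first dose of Lorelco or placebo.

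**Step 3: inflation of the event count (assumed inputs).** Let q be the share of AEs that change grade and k the number of segments in those AEs. Inflation = 1 + q(k - 1).

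- q = 0.10, k = 2: 1 + 0.10 × 1 = 1.10
- q = 0.30, k = 3: 1 + 0.30 × 2 = 1.60

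**Step 4: ratio between arms with equal true event counts (assumed inputs).**

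- q = 0.25 on probucol and 0.10 on placebo, k = 2: 1.25 / 1.10 = 1.14
- Same q, k = 3: 1.50 / 1.20 = 1.25
- Equal q and k in both arms: 1.00

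**Step 5: extra subjects from improving pre-dose AEs (assumed inputs).** With 314 / 2 = 157 per arm, a share of 1% gives 157 × 0.01 = 1.6 subjects and 5% gives 157 × 0.05 = 7.9, so about 2 to 8 per arm.

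**The case against.** The strongest reply is that rules for collapsing records, taking the worst grade and handling carried-over events usually sit in the SAP. Section 13 defers detailed methods to an SAP that is not at hand. Section 12.4 also requires matching end and start times and speaks of a single AE with continuous duration, so the segments can be rejoined; on this view it is a data-capture convention, not a counting rule. This stands in part. The data would support correct counting, so double counting in the final tables is a consequence of the text and not a certainty. But the protocol itself fixes the recording rule, the TEAE definition and the measures. An SAP that follows them as written gives the wrong count, and one that corrects it has to depart from the instruction that each change is a separate AE.

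Three further objections stand and set the limits of the point.

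- A reader might infer that AE incidence as a whole is miscounted. It is not: the number and percentage of subjects per term comes first in the summaries, and splitting within a subject and term leaves it unchanged.
- A reader might infer that any condition present before treatment becomes a TEAE when it eases. Section 12.3 sends most of these to medical history, where easing creates no AE record.
- A reader might infer a bias between arms. Both arms follow the same rule, so a bias needs grade changes to differ by arm. A longer event adds no record unless its grade changes.

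The protocol also calls its analyses mainly descriptive, without formal tests, and ties no decision rule to a TEAE count.

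**Conclusion.** The point holds as a fault in the event count, the severity summary and the breadth of the TEAE definition. Taken as written, each on-treatment grade change adds one TEAE to the count, so a Grade 1-2-1 episode is three. A pre-dose AE that only improves becomes one TEAE instead of none and adds a subject, but this route is narrow.

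The size cannot be found from the documents. The inflation of 1.10 to 1.60, the arm ratios of 1.14 and 1.25, and the 2 to 8 subjects per arm all rest on assumed rates. The ratios merely restate the imbalance put in. The documents do not support the stronger conclusions that the arms will be compared unfairly or that the safety endpoint as a whole is invalid. Efficacy and sample size are unaffected. This is a minor safety-reporting correction, worth making because it is cheap.

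**What to change.** - **12.4:** keep the split records, for listings.
- **13.4:** state that contiguous records of the same event, chained by the matching end and start times that 12.4 already requires, count as one AE at its worst on-treatment grade, in both the number of TEAEs and the severity summary.
- **12.3 and 13.4:** use one definition: a TEAE is an AE that starts, or increases in grade, at or after first dose. An AE present before first dose that stays the same or improves is then not a TEAE.
- **eCRF (optional):** a field linking the segments of one event. The matching times already allow chaining, so this is a convenience.

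The cost is a sentence in each of these sections and minor programming. The downside is that grade fluctuation within an event is visible only in the listings.

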12.5 Reporting of SAEs and SUSARs

In accordance with ICH guidelines for GCP, a copy of the written report of any SAEs should promptly be sent to the study Sponsor. The Investigator must notify the study Sponsor (or the Sponsor designated study Safety Officer) within 24 hours of becoming aware of the occurrence of an SAE.

Information regarding SAEs will be transmitted to the Sponsor (or the designated study safety officer) using an SAE Form as described in the study Safety Reporting Plan. The SAE Form must be completed and signed by a member of the Investigational staff and transmitted to the Sponsor (or the designated study Safety Officer) within 24 hours (Table 9). Any new or updated clinical information on the SAE will be recorded on a new SAE form and sent to the Sponsor designated study Safety Officer within 24 hours of the information being available. The initial and follow-up reports of an SAE should be made by e-mail.

Table 4. Contact details for transmission of SAE reporting forms to the Sponsor designated Safety Officer.

Sponsor designated safety	Name: [name]
officer details for SAE	[contact]
reporting	Email: [contact]

The Investigator must report SAEs to the appropriate Human Research Ethics Committee that approved the protocol unless otherwise required and documented by the Ethics Committee.

It is the responsibility of the Sponsor to determine whether a reported SAE fits the classification of a SUSAR. The Investigator's opinion regarding the assessment of expectedness (if provided) and causality will be taken into account in the Sponsor's determination of the SAE as a SUSAR. The causality assessment given by the Investigator cannot be downgraded by the Sponsor.

SAEs (and SUSARs) will be reported to competent authorities in accordance with national

Protocol Version 4, 06 OCT 2021

Confidential

Page 46 of 70

requirements. The Sponsor assumes responsibility for appropriate reporting of SAEs (and SUSARs) to the regulatory authorities.

12.6 Follow-up of AE and SAE

After the initial AE/SAE report, the Investigator is required to proactively follow each patient and provide further information to the Sponsor on the patient's condition.

All AEs and SAEs documented at a previous visit/contact and are designated as ongoing, will be reviewed at subsequent visits/contacts. Adverse events and SAEs that have not resolved by the end of the study, or that have not resolved upon discontinuation of the patient's participation in the study, must be followed until any of the following occurs:

- The event resolves;
- The event stabilizes;
- The event returns to Baseline, if a Baseline value is available;
- The event can be attributed to agents other than the study drug or to factors unrelated to study conduct;
- It becomes unlikely that any additional information can be obtained (patient or health care practitioner refusal to provide additional information, lost to follow-up after demonstration of due diligence with follow-up efforts).

The Investigator will ensure that AE/SAE follow-up includes any supplemental investigations as may be indicated to elucidate the nature and/or causality of the event. This may include additional laboratory tests or investigations, histopathological examinations, or consultation with other health care professionals.

The Sponsor may request that the Investigator perform or arrange for the conduct of supplemental measurements and/or evaluations to elucidate as fully as possible the nature and/or causality of the AE/SAE. If a participant dies during participation in the study or during a recognised follow-up period, where possible, the Sponsor will be provided with a copy of any post-mortem findings, including histopathology.

Due to the coronavirus SARS-COV-2 (COVID-19) pandemic, Investigators must also ensure compliance with local governing legislation and reporting requirements associated with COVID-19 infections.

12.7 Exposure In Utero Management and Reporting

In instances of pregnancies or suspected pregnancies (including a hCG pregnancy test > 25 U/L regardless of age) while a patient is on study treatment, dosing of Lorelco TM (and placebo) must be discontinued immediately. Pregnant patients (or pregnant partners of male patients) should be advised to call their healthcare provider.

The Investigator will notify the Sponsor and designated study Safety Officer of any pregnancy and document the pregnancy on the Exposure in Utero Form as described in the study Safety Reporting Plan.

The Investigator shall obtain informed consent from a pregnant patient (or a pregnant female partner of a male patient) to allow the Investigator (or delegate) to conduct follow-up throughout the gestational period and on the infant following delivery. The Investigator shall follow-up newborn infants that have been exposed to study drug *in utero* for a minimum of 12 months. Upon discovery of any congenital anomalies (or neonatal deaths) the Investigator

Protocol Version 4, 06 OCT 2021

Confidential

Page 47 of 70

shall submit a follow-up report to the Sponsor (or designated study Safety Officer) using an SAE Form (as per the study Safety Reporting Plan) including information regarding the status of the newborn. A miscarriage or abortion shall also be reported by the Investigator to the Sponsor (or the designated study Safety Officer) using an SAE Form.

12.8 Data Safety Review Committee

A Data Safety Monitoring Board (DSMB), comprised of external parties, has been established for the PIA-Study. Indicated are experienced clinical researchers in geriatric medicine; cardiology and electrophysiology; lipid, stroke and general medicine; cardiovascular medicine and clinical trials; and in data management. The DSMB will initially meet on a quarterly basis (twice) followed by 6-monthly meetings unless deemed required more often. Additional meetings will be held as required on ad hoc basis. To address the risk of QT/QTc prolongation, ECG safety monitoring will be completed and read on site by the study doctor during screening and study visits at baseline and weeks 3, 4, 5, 15, 26, 39, 52, 65, 78, 91, 104, and 4 weeks following completion of the study. Measurement of OT/OTc interval will be completed using automatic algorithms and manual measurement (to the nearest 5 milliseconds and referencing to normal values)²⁰. In the event of a severe adverse effect, such as prolonged QT interval, blinded high quality ECG data will be made available for review by the DSMB. In addition, ECG data will be reviewed by the DSMB 3 monthly (initially) and will be blinded to time, treatment, and subject identifier. Correction of QT interval will be determined using Fridericia's correction: QTcF=QT/RR1/3. Absolute QTc interval prolongation (> 500 ms) and change from baseline in QTc interval (> 50ms) will also be used in consideration for discontinuation or change in treatment protocol. As heart rate can influence corrected OT interval (potential for both over, or under-correction), it is important to ensure that the participant is at rest before and during the ECG. The study doctor will ensure a short rest period prior to administering the ECG to ensure altered heart rate is not a potential confounding factor in QT interval analysis. Furthermore, to ensure interpretation of QT/QTc interval data is correct, the QT/QTc interval data will be analysed using both analyses of central tendency (e.g., means, medians) and categorical analyses (e.g., absolute QTc interval prolongation, change from baseline in QTc interval). If a participant is prescribed a second or subsequent drug with potential QTc prolongation while taking probucol, additional ECGs will be completed to monitor the risk of QTc prolongation. In the event of a severe adverse event, or if prolonged QT/QTc interval continues following discontinuation of LorelcoTM, participants may be referred to a cardiologist.

Furthermore [name] (Clinical Professor of Medicine, University of Western Australia and Hollywood Hospital, Western Australia), a leading expert in managing patients with cardiac arrhythmia's will serve as an Associate Investigator for this study and will ensure the study doctor is trained and quality assured in assessing QT/QTc interval, and will review eligibility for participation and safety reports when required.

Participants will be provided with a list of potential side effects of the treatment medication and will be advised to contact the study doctor should any side effects occur. Participants will also be instructed to call 000 should they experience an allergic reaction to the treatment drug. Additionally, participants will be advised to seek immediate medical attention if symptoms such as light-headedness, dizziness, palpitations, shortness of breath, or fainting occurs. The study doctor will also phone participants at week 3, 4, 6, 20, 29, 47, 55, 73 and

Protocol Version 4, 06 OCT 2021

Confidential

Page 48 of 70

Curtin University Study Protocol
Protocol No.: PIA-2020

81 to discuss if the participant has experienced any side effects. If side effects are noted by the participant, continuation of the study will be determined on a case by case basis by the study doctor. Participants will also be required to attend safety evaluation appointments at approximately week 3, 4, 5, 15, 26, 39, 52, 65, 78, 91, 104 and approximately 4 weeks following the end of the study. These sessions will be to monitor potential side effects and/or adverse events.

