4.4 Risk Assessment and Guidance for Investigators

Prolongation of the QT interval can occur in patients on probucol. Clinical trials by Yamashita¹⁰ and Kang¹¹ reported significantly more prolonged QT interval adverse events in individuals taking probucol (LorelcoTM), compared to controls. While drug-induced prolonged QT interval can be associated with significant adverse side effects such as ventricular arrhythmia (torsades de pointes), studies involving the use of 500 mg of Probucol daily, reported probucol-induced prolonged QT interval was not associated with, or increased the incidence of, ventricular arrhythmias. Furthermore, Walldius¹² reported that there was no significant difference in cardiovascular clinical events between individuals taking probucol and controls. No malignant arrhythmias or torsades de pointes were reported for either group. The absence of arrhythmias may be due to strict prolonged QT/QTc interval exclusion

Protocol Version 4, 06 OCT 2021

Confidential

Page 19 of 70

criteria. While there is no consensus on upper limit corrected QT/QTc interval values, many studies adopt an absolute QT/QTc interval prolongation of > 500ms. This reduces the risk of ventricular arrhythmia, as participants are discontinued prior to prolonged QT intervals associated with arrhythmia.

While QT prolongation by probucol may not enhance the occurrence of lethal ventricular arrhythmias, studies have identified several clinical risk factors for drug-induced arrhythmias, including probucol. These include;

- Cardiac factors (including congenital long QT syndrome, family history of sudden cardiac death, bradycardia)
- Myocardial hypertrophy
- Heart failure
- Liver disease
- Thyroid Dysfunction
- Renal or hepatic impairment

The above clinical risk factors should be considered prior to treatment with probucol¹³.

Further information regarding Lorelco $^{\text{TM}}$ is available in the Investigator's Brochure.

Protocol Version 4, 06 OCT 2021

Confidential

Page 20 of 70

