6.6 Trial stopping criteria

The trial will be discontinued if one or more of these criteria are indicated:

- Substantial deviations from the approved protocol
- Adverse-effects of unexpected type, severity, or frequency are encountered
- As the trial progresses, the continuation of the trial would disadvantage some of the participants as determined by the CI team/researchers, trial monitors or the DSMB.

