13.8 Interim Analysis

No formal interim analyses are planned at this time. Safety will be reviewed in an ongoing fashion as described in Section 6.

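### The DSMB's periodic ECG review is blinded to time, arm and subject, so it cannot show QTc rises above 50 ms or an arm imbalance; a smaller point is that two QTc baselines are in use

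*Protocol*

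**What the plan says.** **The DSMB's view.** Section 12.8 states that "ECG data will be reviewed by the DSMB 3 monthly (initially) and will be blinded to time, treatment, and subject identifier". After a severe adverse effect such as a prolonged QT interval, "blinded high quality ECG data will be made available for review by the DSMB"; what is masked in that case is not said.

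**The criteria.** Section 12.8 names an absolute QTc above 500 ms and adds that "change from baseline in QTc interval (> 50ms) will also be used in consideration for discontinuation or change in treatment protocol". Section 6.7 applies both limits to individual dosing. Among the grounds for stopping the trial, section 6.6 lists that "the continuation of the trial would disadvantage some of the participants as determined by the CI team/researchers, trial monitors or the DSMB".

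**The known risk.** Section 4.4 cites two trials that "reported significantly more prolonged QT interval adverse events in individuals taking probucol" compared with controls.

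**Other safety review.** Section 13.8 plans no formal interim analysis and says "Safety will be reviewed in an ongoing fashion as described in Section 6". In Section 6, part 6.1 has the SRC review AEs, clinical findings and laboratory results before dosing goes beyond the first thirty patients.

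**Baselines.** Section 6.7 measures the 50 ms rise from the mean of screening and baseline Day 1. Section 13.4 takes changes in ECG parameters from the last assessment before the first dose of Lorelco or placebo. Section 12.8 lists ECGs at "screening and study visits at baseline and weeks 3, 4, 5" and later visits, so it treats baseline as separate from Week 3. The ECG row of Appendix 1 is marked at screening and at Week 3 Day 1 and is blank at Visit 0.

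**The concern.** QT prolongation is the main identified risk of this drug, and the evidence in 4.4 is a difference between probucol and control. A safety board asked whether continuing disadvantages participants needs to see that difference, and needs to see whether patients are drifting upward from their own starting values. Section 12.8 does not merely leave the format of the DSMB's ECG data open. It states a blinding that removes the labels needed for both questions. Masking time, arm and subject is sound practice for the person who measures a tracing; it is a poor rule for the body that oversees the trial.

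The baseline point is smaller. If the rule that stops dosing and the tables that report QTc change start from different reference values, the report need not agree with the decisions taken during the trial.

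**Working it through.** The protocol gives no figure to reproduce on this point. The check is a comparison of sections with some short arithmetic.

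**1. What each question needs, and what the blinding leaves**

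| Question | Information needed | Available in the periodic DSMB review? |
|---|---|---|
| Is QTc above 500 ms? | The value on one tracing | Yes |
| Has QTc risen more than 50 ms? | Two tracings from one subject, with the baseline identified | No: subject and time masked |
| Is QTc longer on one arm? | An arm label, even a coded one | No: treatment masked |

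**2. Other routes by which the DSMB could see the missing information**

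- Event-triggered review (12.8): also blinded, one case at a time, no arm comparison.
- Reinstatement review (6.7 and the synopsis): case by case, so subject-level, but only for patients already discontinued.
- Ad hoc meetings (12.8): allowed, with no data content stated.
- SRC review (6.1): a different body; neither QTc nor an arm split is named.
- Central-tendency and categorical QTc analyses (12.8): planned, with no recipient, timing, arm split or baseline named.

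None of these gives the DSMB QTc by arm over time.

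**3. What an anonymous 500 ms check misses**

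Inputs: the limits of 500 ms and 50 ms (6.7, 12.8), and the entry QTcF ceilings of 450 ms for men and 460 ms for women (7.2, criterion 5). For baseline B, the individual rule is met above B + 50 and the anonymous check flags values above 500. The gap runs from B + 50 to 500, a width of 450 − B.

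- B = 400 (illustrative): from 450 to 500, width 50 ms. Rises of 51 to 100 ms pass the anonymous check.
- B = 450: width 0. Any value above 500 already means a rise above 50.
- B = 460: 500 − 460 = 40, so the 500 ms limit is reached first and nothing is missed.

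The gap therefore affects patients who start below 450 ms and widens as their baseline falls.

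**4. The two baselines**

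Let S be the screening value and D the Day 1 value. Section 6.7 uses (S + D)/2. On the Appendix 1 schedule, the 13.4 baseline is S if the run-in placebo capsule counts as the first dose, and D (Week 3 Day 1) if it does not. Then:

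- (S + D)/2 − D = (S − D)/2
- (S + D)/2 − S = (D − S)/2

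So the baselines differ by half the difference between the two visits, in either direction. Example with S = 400, D = 410 and 457 ms on treatment:

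- 6.7: baseline 405, change 457 − 405 = 52 ms
- 13.4 with D: 457 − 410 = 47 ms
- 13.4 with S: 457 − 400 = 57 ms

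The 5 ms shift equals one step of the manual measurement in 12.8.

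**The case against.** **The blinding sentence may concern only the reading of tracings.** It stands in a paragraph largely about measuring QT, and nothing there says that the DSMB sees nothing else. By-arm closed reports usually sit in a charter, which is not shown. That is a fair reading of the intent, but the words apply the blinding to the DSMB's review itself. A charter that supplied coded-arm ECG data would sit awkwardly with 12.8 until 12.8 is clarified.

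**Patients might seem unprotected.** A reader might infer that nobody can detect a rise above 50 ms. The protocol does not support this. The study doctor reads every ECG on site with both limits in force, an arrhythmia specialist trains and quality-assures that reading, and the DSMB has event-triggered, reinstatement and ad hoc reviews. A reader might also infer from 13.8 that Section 6 contains no ongoing safety review. That is wrong too, because 6.1 describes the SRC review. What is missing is narrower: QTc by arm, and change over time, for the DSMB.

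**The baselines may never collide.** A reader might infer that the report will count patients above 50 ms differently from the stopping rule. Section 13.4 plans values and changes by visit and defines no such count. The categorical analysis in 12.8 names no baseline and could use that of 6.7. A general analysis baseline beside a purpose-built stopping baseline is also common. In addition, 11.5.3 and Appendix 1 (note 5) call for triplicate ECGs at screening and before the first dose, which reduces measurement error in both values. All of this stands and makes the second point minor. It does not remove the difference between a two-visit mean and a single visit, or the unclear Day 1: 6.7, 11.5.3 and 12.8 refer to a Day 1, pre-first-dose or baseline ECG, and Appendix 1 marks none at Visit 0.

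**Conclusion.** The main point holds as a weakness in DSMB oversight, not as a failure of individual protection. From the periodic review that 12.8 describes, the DSMB can check absolute QTc values but cannot see a change above 50 ms or an arm imbalance, and no other section supplies QTc by arm. This follows from the text and needs no assumption. It would be resolved if a charter provides such tables and 12.8 is reworded to allow them. The 400 ms baseline in the working is illustrative; the width 450 − B follows from the protocol's own limits.

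The baseline point also holds, as a minor inconsistency. The half-difference formula assumes that the 13.4 baseline is one of the two visits in the 6.7 mean. Any effect on counts above 50 ms arises only if the categorical analysis in 12.8 uses the 13.4 baseline. Its size depends on within-patient variability, which the protocol does not give, so no patient count is offered here.

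**What to change.** 1. State in 12.8 that blinding to time, treatment and subject applies to the reading and measurement of tracings only.
2. Give the DSMB closed, subject-linked, time-ordered QTcF tables by masked arm (A/B), with counts of QTcF above 500 ms and of changes above 50 ms.
3. Use the 6.7 mean as the baseline for the QTc change summaries and categorical analyses. Name its two ECG visits so that they match Appendix 1: either screening and Week 3 Day 1, or add an ECG at Visit 0.

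The cost is a wording amendment and one closed table per DSMB meeting, prepared by someone outside the blinded study team. The downside is that the DSMB sees masked-arm data. Adding a Visit 0 ECG, if that option is chosen, means one more procedure per patient. Randomisation, sample size and the efficacy analysis are unaffected.
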